METHODOLOGICAL PROCEDURES & DOCUMENTS MANUAL

Reducing Maternal Depression and Promoting Infant
Social-Emotional Health & Development

NIH R01 HD086894

NCT03464630

Randomized Controlled Trial Design: Prior to iPhone set up, the Intervention Project Coordinator implements randomization procedures. Using a random number generator, mother-infant dyads were randomized, in a 1:1 allocation, to one of the two parallel interventions: Mom and Baby Net or Depression and Developmental Awareness. The Intervention Project Coordinator notifies the PI to review condition assignment and assigns case to intervention coach. (see pages 26 and 98 in Procedures below)

Objective and Specific Aims:

The objective of this project was to address the problem of silo interventions and to improve accessibility to intervention that both reduces maternal depression and improves infant social emotional and communication development. To achieve this objective the following specific aims were addressed:

1. Embed core components of the Mom-Net Internet intervention into the Internet based virtual coaching intervention, Baby Net, to create Mom and Baby Net, an instructionally sound program geared to reduce the internal demands of depressed mothers postpartum.
2. Evaluate the impact of the Mom and Baby Net (MBN) program, as compared to a parallel Internet remote coaching intervention: Depression and Developmental Awareness (DDAS), via a randomized controlled trial. Depressed mothers during the postpartum period and their infants (N=180 dyads) will be randomized to the MBN or DDAS . Impact will be examined relative to:
 - 2.1 Change in parenting behavior, attitudes, beliefs, knowledge, and stress;
 - 2.2 Infant social-emotional behavior and development change;
 - 2.3 maternal depressive symptoms change; and
 - 2.4 Concomitant change in parenting, infant social-emotional, and maternal depressive symptom outcomes as a result of intervention.
3. Evaluate moderating influences on parent and infant behavior within the context of depression during the post partum period. We will focus on:
 - 3.1 The extent to which maternal depression prior to intervention, including current depression symptoms as well as depressive history and chronicity, relate to dosage within the MBN program;
 - 3.2 How dosage moderates parent and infant behavioral change as well as maternal depressive symptom change; and

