 - 3.3 The extent to which contextual risks surrounding mothers (maternal isolation, social support and relationship status and conflict) not only relate to maternal depressive symptoms and MBN program dosage/skill acquisition but also moderate parenting, infant, and maternal depressive symptom change.
4. Assess maintenance of the program effects at 1-, 3- and 6-months after intervention. These trajectories for mothers and infants will allow for building a preliminary view of intervention effects as infants move into the next stage of development to determine if intervention early in infancy produces continued positive effects as these infants age.

PROCEDURES & DOCUMENTS TABLE OF CONTENTS

I. Recruitment and Screening.....	page 4
Procedures.....	page 5
Screening Script.....	page 7
Screening Documents.....	page 16
Recruitment Form	
II. Assessment Manual.....	page 17
Consent & Assessment Visit Procedures.....	page 18
Review and Sign Consent.....	page 20
Randomize Participant to Condition.....	page 26
Assessment Visit Documents.....	page 27
Consent Form	
Assessment Summary & Risk Identification	
Assessment Data Checklist iPhone	
Customization Questionnaire	
Resource Materials.....	page 38
Postpartum Depression Facts	
Crisis Help Card	
III. Coach Manual.....	page 68
Training Visit Procedures.....	page 69
Training Visit Documents.....	page 74
iPhone Agreement	
Coach Call Guidelines.....	page 76
Lost Contact Letter.....	page 78
IV. Safety Monitoring Documents.....	page 79
V. Adverse Event Guidelines.....	page 81
Decision Tree	
VI. COVID Remote Procedures*	page 84
Remote Recruitment and Screening Procedures.....	page 85
Remote Assessment and Training Procedures.....	page 95
Randomize Participant to Condition.....	page 98

I. Recruitment and Screening

RECRUITMENT & SCREENING PROCEDURES

RECRUITMENT PROCEDURES

Referrals from sites

Referral sites will be given referral materials to distribute to eligible participants. Eligible participants are mothers of babies age 0 – 12 months who live in the metro-Atlanta area, speak English, and meet criteria of depression on approved depression screening. Some sites will refer moms without screening for depression based on mom's age, location, and baby's age eligibility criteria. They will use the parent letter specific to sites that are not screening for depression.

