 - a. *I will email you a copy of the project's consent form. This document will explain in detail the purpose of the Mom and Baby Net project, what you will be doing in the project, and how we will keep your information safe. We are taking necessary precautions to keep you, your family, and our staff healthy during the Coronavirus pandemic. The Pre-assessment and training visits will be conducted remotely using Zoom – an app that allows us to have a video call. I will later explain how Zoom works if you choose to participate.*
 - b. *The iPhone agreement form will also be emailed to you. This document covers expectations of loaning you the iPhone to complete the Mom and Baby Net project. Your phone service will be covered while you are participating in the program. We will monitor your progress on a month to month basis. If you are making progress and staying in communication with your coach, we will renew your service for the next month. If we lose contact with you, or you are not making progress in the program, your phone service may be discontinued; If we cannot reach you and your phone is not returned, it will be reported as lost or stolen.*
 - c. *I will also mail a copy of both of these forms to your home. Have you still been receiving mail and packages as usual during this time?*
 - d. *What questions do you have? [answer any questions]*
 - e. *The next step is to schedule a call to talk about the Consent and iPhone agreement forms after you receive them in the mail. You will do this call with your Coach, who will be with you for the rest of the program. She will go over both of these forms, answer any questions you have, and explain the next step which will be sending the iPhone and materials to you. Please think about a time where you will be able to talk for about 15 minutes and she will reach out tomorrow to schedule that call.*

3. Confirm email and mailing address

After Consent Scheduling Call

1. Assign participant ID and enter into Access
2. Notify coach ASAP to reach out to participant to schedule consent call.
3. Mail & email Consent and iPhone agreement
 - a. Note to add in email/envelope: We will review these documents on our next call. After all your questions are answered, you will sign them, take a picture of each signature page, and will text them to the project staff member who you speak with on that call.

Day Before Consent Call

1. Call or text mom to confirm she received the consent & iPhone agreement in the mail

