 - iv. Make a note of where mom ended (ideally mark the page if you have the PDF printed)
 - v. About 4 hours after you end the call, check Qualtrics to make sure the incomplete survey submitted.
 1. Log into Qualtrics
 2. Find survey that was partially completed
 3. Click on 3 dots to the right of that survey and click 'Data & Analysis'
 4. Look for mom's ID # and info for that survey to confirm submission; if not there yet, wait a little while and refresh to check again
 - vi. Restart survey the next day
 1. Before starting call again with the mom, log into Qualtrics
 2. Find survey that was partially completed
 3. Click on 3 dots to the right of that survey and click 'Data & Analysis'
 4. Find mom's partially completed survey (by ID and date)
 5. On that line, to the very right, click the arrow under the 'Actions' column
 6. Click 'Retake Response' (do NOT click 'Retake as New Response')
 7. A box will pop up with a link – this is the link you will send to the mom

8. When she clicks on the link, the survey will open to the first page (ID, mom initials, etc.) but should be completed already. Instruct her to click through until she reaches the page where she left off.
9. Review the instructions again for the section she is on.
10. Continue as usual through the rest of the survey.

6. End of program information

- a. Follow-ups and video release
 - i. *The last thing we ask moms to complete is one follow-up. We will not have to see you for these. 6 months after today, you will get an email that has a link to a 5-10 minute survey. If you do not complete the survey on your own, we will follow up via phone to remind you and you can do it over the phone if you want. Do you have any questions about the follow up? I will also send you the date for your follow up through Coach Talk.*
 - ii. *I am sending you a link now to a form. Please let me know when you get it and I will go through it with you.*
 1. Send mom link the same way survey links were sent
 2. bit.ly/MBNpostInfo
 - iii. *Once mom has form open: First, we need the best email address to reach you. This is where the follow-up email will come 1 month from today.*
 - iv. *Next, please put the best phone number, other than the project phone number, to reach you. Then you can click to the next page.*

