9. Update Matriculation table

- a. Assessment tab: Mark post assessment completed (Y)
- b. Training tab: enter date of post assessment and length of time in program

10. Project coordinator will complete

- a. Matriculation table
 - i. Mark model release signed (Y or N)
 - ii. Enter follow up assessment dates
- b. Project calendar
 - i. Enter follow up dates
- c. Download survey PDFs and save to participant folder
- d. Update follow up contact info (email & phone)
 - i. Access
 - ii. Qualtrics

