Statistical Analysis Plan

Title: Reducing Maternal Depression and Promoting Infant Social-Emotional Health & Development

NCT03464630

Date: 09/18/2016

Analytic Strategy

Constructs. We will use a systematic approach to construct development to create two parent outcomes (mother positive/negative) and one infant outcome (infant social emotional functioning). *For our outcomes of maternal depression, parenting knowledge and stress, we will examine single indicants. To view potential intervention moderating effects, we will attempt to create a maternal contextual risk indicant (e.g., isolation/support, relationship status, conflict, economic hardship); for maternal depression prior to intervention as a potential moderator, we will view depression onset, chronicity, and severity as well as presence of other treatment including medication to examine each of these and their effect on intervention outcomes.* For factor analysis, given appropriate internal consistency and inter-rate reliability, we will examine questionnaire scales and observational codes using factor analytic techniques [99], retaining a 5:1 subject to parameter ratio. Scale factor loadings above .30 and communality estimates above .15 will be confirmed within SEM methodology to produce fit indices to view how each indicant set fits into their specified domain. If satisfactory, unit-weighting of the standardized score for each indicant will be summed. If not, we will select an index variable within each domain to represent the outcome.

Random Sampling/Attrition Analysis. Though mother-infant pairs will be randomly assigned to the intervention, condition differences may exist due to random sampling failures or differential attrition. To address this issue, 2×2 (Group x Attrition Status) MANOVAS will be performed using the baseline assessment for mother, infant and contextual risk variables. The presence of a statistically significant Group main effect would provide evidence that random assignment was not effective in equating groups. A second possible source of nonequivalence is differential attrition by condition. A Group x Attrition Status significant interaction provides evidence of differential attrition between groups. In general, analyses will proceed using an “intent to treat” approach and all participants recruited will be included in subsequent analyses.

Examination of Acute Intervention Effects (Aim 2)

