(Aims 2.1 - 2.3) Our post-assessment n, to examine acute intervention effects, is expected to be 150 (75/condition). We will initially view intervention effects on our mother/infant outcomes using a 2 (pre-post) $\times 2$ (MBN intervention group) repeated measure analysis of variance. We will examine the inter-correlations among outcomes and, if significant, will use a MANOVA approach to examining MBN intervention effects. The F test is robust to non-normality if such non-normality is caused by skewness rather than outliers. We will take appropriate measures to reduce outlier influences. **(Aim 2.4)** To examine the relations between mother change (parenting and maternal depression) and infant change, one approach will be to create individual beta estimates for mothers and infant utilizing the polynomial contrast function within MANOVA to produce individual trajectory scores reflecting parent and infant change from pre to post that can then be used in external between-condition covariate analysis. The trajectory scores will be subjected to an analysis of covariance with infant change trajectories as the dependent variable and parent change as the covariate. We will determine whether the parent change covariate is significantly related to the dependent variable (demonstrating that changes in parenting behavior and child functioning covary). We will determine the statistical significance and effect sizes of intervention effects (ignoring the covariate). We will then determine if entering the parent functioning covariate modifies the intervention effect size and statistical significance. If parent change is strongly linked to infant change, then entering the covariate should result in nonsignificant intervention effects. Estimates of covariance-adjusted effect sizes will provide estimates of the proportion of intervention effect size that can be explained by the parenting change variable. We will test for between-group heterogeneity of covariance to determine whether the strength of association between change in parenting and infant functioning differs by intervention group.

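### In the manual supplied, every step that sets up a follow-up depends on the post-assessment call, so a mother who misses that call has no written route into the Aim 4 data

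*Protocol*

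**What the plan says.** **Aim and population.** Aim 4 in the protocol (Objective and Specific Aims) is to "Assess maintenance of the program effects at 1-, 3- and 6-months after intervention". The SAP (Random Sampling/Attrition Analysis) describes an intent-to-treat approach in which "all participants recruited will be included in subsequent analyses".

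**How a follow-up is set up.** The only procedure in the supplied text is in Section VI of the manual, under the remote post-assessment procedures:

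- *Clock.* In End of program information, the coach tells the mother on the call: "6 months after today, you will get an email that has a link to a 5-10 minute survey". If she does not complete the survey, staff follow up by phone.
- *Contact route.* A form opened on the same call asks for her details: "First, we need the best email address to reach you". It then asks for a phone number other than the project phone.
- *Calendar entry.* Among the coordinator's steps after the post call is: "Enter follow up assessment dates". The same list has the coordinator update her email and phone in Access and Qualtrics.

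**What is held earlier.** The tracking form has an email field. The remote consent-scheduling call includes the step "Confirm email and mailing address". Alternate contacts are taken at the recruitment call and updated at training.

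**Mothers who stop.** The lost-contact letter in the Coach Manual offers the choice of ending the intervention and doing the post-assessment. The remote procedures schedule post at session 14 or at whichever coach call is the last.

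**Sample sizes.** In the SAP, the post-assessment n "is expected to be 150 (75/condition"). The maintenance sample is put at no fewer than 150, with 17% overall attrition.

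**The concern.** In an operating manual, what gets done is what has a date and a trigger. Here the date, the follow-up contact form and the calendar entry all arise in or after the post call. A mother who has no post call has none of them, and nothing in the text prompts staff to send her the survey. Her project phone service may also have been stopped, because the remote scripts allow that when contact is lost.

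Two things are at stake for Aim 4:

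- **Representativeness.** Completing post happens after randomisation and may be related to arm and to depression. A maintenance comparison limited to post-completers is not a comparison of the randomised arms. Mothers without a post would bring at most a baseline value to the planned growth model, and so almost no information on change.
- **Precision.** The post-assessment is two remote calls of about an hour each, with videos. The follow-up is a 5-10 minute survey by email. Making the short assessment conditional on the long one gives up data that could be collected cheaply.

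**Working it through.** **Inputs**

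| Input | Value | Source |
|---|---|---|
| Randomised | 180 dyads, 1:1 | Protocol, Aim 2 |
| Attrition to post | 17% (n = 150) | SAP, Power Analysis |
| Maintenance sample | at least 150 | SAP, Maintenance of Effects |
| Sponsor's earlier study | 7% lost by post, 15% by 6 months | SAP, Power Analysis |
| Growth-model guideline | 5 cases per parameter; 34 parameters | SAP, Power Analysis |

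**1. The plan's figure.** 180 × (1 − 0.17) = 149.4, so the stated 150 reproduces. The number without a post is 180 − 150 = 30 (30/180 = 16.7%).

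**2. What equal figures imply.** If only post-completers enter follow-up, the maintenance sample cannot exceed the post sample. The stated minimum of 150 is then also the maximum, and is reached only with no loss after post.

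**3. Loss after post.** Reading the earlier study's 15% as cumulative from baseline, retention from post to 6 months is 0.85/0.93 = 0.914.

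- 150 × 0.914 = 137.1, or 76% of 180 (24% overall loss).
- If the 15% were instead counted from post, the result is 150 × 0.85 = 127.5.
- For assumed further losses of 5%, 10% and 20%, the results are 142.5, 135 and 120.

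**4. What following the other 30 would add.** The documents give no response rate for these mothers, so it is an assumption.

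| Share of the 30 who answer | Dyads with 6-month data | Share of 180 |
|---|---|---|
| none | 137 | 76% |
| one third (10) | 147 | 82% |
| one half (15) | 152 | 84% |
| all | 167 | 93% |

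Reaching 150 needs 150 − 137.1 = 12.9, or about 13 of the 30.

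**5. Growth-model sizing.** At 5:1, 34 parameters need 34 × 5 = 170 cases. By the same rule 150 cases support 30 parameters and 137 support 27. The 34 therefore does not match the SAP's own 150, whatever is decided on follow-up.

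**6. Timing.** The protocol aim gives 1, 3 and 6 months. The post-call script describes a single follow-up at 6 months and, a few lines later, says the follow-up email will come 1 month after the call. No date can be entered for any mother until these are reconciled.

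**The case against.** The strongest objection is that this turns silence into a rule. The script is what a coach says to a mother who is on the post call, so it naturally counts from that day. The coordinator's step is worded as an update, which implies that contact details are already on file. The text is the remote script only: no in-home post or follow-up script is supplied, and the consent pages, which might describe follow-up, were removed before review. This stands as far as it goes. A reader might infer that every mother who stops is dropped or has no chance of follow-up, and the documents do not say that. Stopping is also not the same as missing post, since the letter and the last-call rule both lead mothers who stop towards a post-assessment. What remains is narrower: the letter deals with non-reply by closing the intervention and does not mention follow-up, and no other text gives a route.

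On size, adding 10 to 15 mothers to the full 150 would suggest 160 to 165 (89% to 92%). That allows for non-response among the added mothers but assumes none among the post-completers. The response rate itself is uncertain, because mothers who receive the letter have already not answered coach notes or calls.

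It is also fair to say that 150 at 6 months is not unreasonable in itself. At the earlier study's rates, 180 × 0.93 = 167 would reach post and 180 × 0.85 = 153 would reach 6 months. The difficulty arises because the SAP plans for 17% loss already at post.

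Finally, the SAP treats maintenance with caution and as a preliminary view, and it plans a Group × Attrition Status check at baseline. The first limits the consequences. The second can show differential loss but does not recover the missing outcomes.

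**Conclusion.** The concern holds in a limited form. In the supplied manual, follow-up is created only through the post call, and mothers without one have no written route to it. Followed as written, Aim 4 would be answered among post-completers, which does not match the SAP's intent-to-treat statement.

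Taking the SAP's 17% loss at post and the earlier study's retention after it, about 137 of 180 would have 6-month data against a stated minimum of 150. Following the remaining 30 would bring this to about 147 to 152 if one third to one half responded. These figures rest on three assumptions: the earlier study's 15% is cumulative, its retention carries over to this trial, and the response rate is as assumed.

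The change is worth making but is not critical. A reader might infer that the acute (Aim 2) result is compromised. The documents do not support that, because the pre-post analysis does not use the follow-up survey.

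**What to change.** 1. **Reconcile the follow-up times** between the protocol aim and the two statements in the post-call script.
2. **Enter follow-up dates for every mother at randomisation.** Where post takes place, keep its date as the anchor. Otherwise use a prespecified nominal end of the 14-session schedule, counted from the training date. If she was never trained, count it from the randomisation date. This fallback is needed because randomisation comes before iPhone set-up and therefore before training.
3. **Collect the best email and a non-project phone at consent or training**, and re-confirm them at post.
4. **Send the survey, with the phone reminder already planned, to every mother** who has not withdrawn consent for contact.
5. **State in the SAP** that the Aim 4 growth model uses all available data by full-information maximum likelihood, including dyads with a baseline and a follow-up but no post. In the remote pathway randomisation is listed before the pre-assessment calls, so say also how a dyad without a baseline is handled.
6. **Restate the expected maintenance sample** with an explicit allowance for loss after post, and align the 34-parameter figure with it.

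The cost is procedure wording, earlier calendar entries and, at the planned attrition, about 30 more mothers to email and remind at each follow-up. No new assessment or staff is needed. The drawbacks are some unanswered reminders and, for these mothers, a nominal rather than actual end date. Time since last exposure will therefore vary more among them, and the report should say so.
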